## 5.4 Screen Failures

Screen failures are defined as participants who consent to participate in the clinical study, but are not subsequently enter the run-in epoch in the study. A minimal set of screen failure information is required to ensure transparent reporting of screen failure participants to meet the Consolidated Standards of Reporting Trials (CONSORT) publishing requirements and to respond to queries from regulatory authorities. Minimal information includes demography,

screen failure details, eligibility criteria, and any AEs or SAEs meeting reporting requirements as outlined in the data entry guidelines.

### **5.5 Run-in Failure**

For participants successfully screened but discontinued during the treatment run-in period must be carefully documented with the reason in the appropriate CRF, and these participants are considered treatment run-in failures.

No re-screening of participants that are discontinued from the run-in period will be allowed.

### **5.6 Participant Replacement Strategy**

A participant who discontinues from study intervention will not be replaced.

## **6 STUDY INTERVENTION**

Study intervention is defined as any investigational intervention(s), marketed product(s), placebo, or medical device(s) intended to be administered to a study participant according to the study protocol.

Clinical supplies [study intervention(s) provided by the Sponsor] will be packaged to support enrollment . Clinical supplies will be affixed with a clinical label in accordance with regulatory requirements.

### **6.1 Study Intervention(s) Administered**

The study intervention(s) to be used in this study are outlined in [Table 2](#).

Each assigned study interventions will be administered orally once daily. As there is no recommended dosing time, the participant should take their treatment at a consistent time each day and participants are suggested to avoid taking the study intervention with other concomitant medications at the same time. On the visit day, the participant should take the medication after all procedures are completed.

Table 2 Study Interventions

During active run-in period:

Cohort Name	Cohort Type	Intervention Name	Type	Dose Formulation	Unit Dose Strength(s)	Dosage Level(s)	Route of Administration	Regimen/ Treatment Period	Use	IMP/N IMP	Sourcing
A	Active Comparator	atorvastatin	Drug	Tablet	10 mg	10 mg QD	Oral	Run-in period/ 5 weeks	Active treatment to select uncontrolled participants	NIMP	Provided centrally by the Sponsor
B	Active Comparator	atorvastatin	Drug	Tablet	20 mg	20 mg QD	Oral	Run-in period/ 5 weeks	Active treatment to select uncontrolled participants	NIMP	Provided centrally by the Sponsor
Definition Investigational Medicinal Product (IMP) and Non-Investigational Medicinal Product (NIMP) is based on guidance issued by the European Commission. Regional and/or Country differences of the definition of IMP/NIMP may exist. In these circumstances, local legislation is followed.											

During double-blinded treatment period:

Arm Name	Arm Type	Intervention Name	Type	Dose Formulation	Unit Dose Strength(s)	Dosage Level(s)	Route of Administration	Regimen/ Treatment Period	Use	IMP/ NIMP	Sourcing
A1	Experimental	MK-0653C FDC (ezetimibe 10 mg + atorvastatin 10 mg)	Drug	Tablet	10 mg / 10 mg	10 mg / 10 mg QD	Oral	Randomization treatment: 12 weeks	Experimental	IMP	Provided centrally by the Sponsor
	Placebo	Placebo atorvastatin	Drug	Tablet	0 mg	0 mg QD	Oral	Randomization treatment: 12 weeks	Dummy with study treatment	NIMP	Provided centrally by the Sponsor
A2	Active Comparator	atorvastatin	Drug	Tablet	20 mg	20 mg QD	Oral	Randomization treatment: 12 weeks	Active control	NIMP	Provided centrally by the Sponsor
	Placebo	Placebo of MK-0653C FDC (ezetimibe 10 mg + atorvastatin 10 mg)	Drug	Tablet	0 mg	0 mg QD	Oral	Randomization treatment: 12 weeks	Dummy with study treatment	NIMP	Provided centrally by the Sponsor
B1	Experimental	MK-0653C FDC (ezetimibe 10 mg + atorvastatin 20 mg)	Drug	Tablet	10 mg / 20 mg	10 mg / 20 mg QD	Oral	Randomization treatment: 12 weeks	Experimental	IMP	Provided centrally by the Sponsor
	Placebo	Placebo of atorvastatin	Drug	Tablet	0 mg	0 mg QD	Oral	Randomization treatment: 12 weeks	Dummy with study treatment	NIMP	Provided centrally by the Sponsor

Arm Name	Arm Type	Intervention Name	Type	Dose Formulation	Unit Dose Strength(s)	Dosage Level(s)	Route of Administration	Regimen/ Treatment Period	Use	IMP/ NIMP	Sourcing
B2	Active Comparator	atorvastatin	Drug	Tablet	20 mg	40 mg QD	Oral	Randomization treatment: 12 weeks	Active control	NIMP	Provided centrally by the Sponsor
	Placebo	Placebo of MK-0653C FDC (ezetimibe 10 mg+atorvastatin 20 mg)	Drug	Tablet	0 mg	0 mg QD	Oral	Randomization treatment: 12 weeks	Dummy with study treatment	NIMP	Provided centrally by the Sponsor
Definition Investigational Medicinal Product (IMP) and Non-Investigational Medicinal Product (NIMP) is based on guidance issued by the European Commission. Regional and/or Country differences of the definition of IMP/NIMP may exist. In these circumstances, local legislation is followed. The first dose of trial treatment will be administered at the trial site at Visit 4. Subsequent dosing will be performed once daily by the participant (i.e., unsupervised at his/her home) at approximately the same time each day.											

All supplies indicated in [Table 2](#) will be provided per the "Sourcing" column depending upon local country operational requirements. If local sourcing, every attempt should be made to source these supplies from a single lot/batch number where possible (e.g., not applicable in the case where multiple lots or batches may be required due to the length of the study, etc).

Refer to Section 8.1.8 for details regarding administration of the study intervention.

All placebos were created by the Sponsor to match the active product.

## **6.2 Preparation/Handling/Storage/Accountability**

### **6.2.1 Dose Preparation**

There are no specific calculations or evaluations required to be performed in order to administer the proper dose to each participant. The rationale for selection of doses to be used in this study is provided in Section 4.3.

### **6.2.2 Handling, Storage, and Accountability**

The investigator or designee must confirm appropriate temperature conditions have been maintained during transit for all study intervention received, and any discrepancies are reported and resolved before use of the study intervention.

Only participants enrolled in the study may receive study intervention, and only authorized site staff may supply or administer study intervention. All study interventions must be stored in a secure, environmentally controlled, and monitored (manual or automated) area in accordance with the labeled storage conditions with access limited to the investigator and authorized site staff.

The investigator, institution, or the head of the medical institution (where applicable) is responsible for study intervention accountability, reconciliation, and record maintenance (ie, receipt, reconciliation, and final disposition records).

For all study sites, the local country Sponsor personnel or designee will provide appropriate documentation that must be completed for drug accountability and return, or local discard and destruction if appropriate. Where local discard and destruction is appropriate, the investigator is responsible for ensuring that a local discard/destruction procedure is documented.

The study site is responsible for recording the lot number, manufacturer, and expiry date for any locally purchased product (if applicable) as per local guidelines unless otherwise instructed by the Sponsor.

The investigator shall take responsibility for and shall take all steps to maintain appropriate records and ensure appropriate supply, storage, handling, distribution, and usage of study interventions in accordance with the protocol and any applicable laws and regulations.

## 6.3 Measures to Minimize Bias: Randomization and Blinding

### 6.3.1 Intervention Assignment

Intervention allocation/randomization will occur centrally using an interactive response technology (IRT) system. There are 2 cohorts with 2 study intervention arms in each cohort. Algorithm of participant's allocation is based on current statin dose prior to the screening (a stable dose is required at least 4 weeks prior to Visit 1). For participants who is currently treated with atorvastatin 10 mg or equivalent or equivalents less than 10 mg atorvastatin will be assigned to cohort A; while other participants who is currently under treatment of 20 mg atorvastatin or equivalents will be assigned to cohort B (atorvastatin and other equivalent statin can be found in [Table 3](#)). Within each cohort, participants will be assigned randomly in a 1:1 ratio to receive MK-0653C or atorvastatin treatment, respectively.

Table 3 Dose of Atorvastatin and Other Equivalent Statin

Cohort	Atorvastatin (mg)	Simvastatin (mg)	Lovastatin (mg)	Pravastatin (mg)	Fluvastatin (mg)
A	-	10	20	20	40
A	10	20	40	40	80
B	20	40	80	-	-

### 6.3.2 Stratification

Intervention allocation/randomization will be stratified according to the following factors:

- Cohort (i.e., Cohort A – atorvastatin  $\leq$ 10 mg or equivalent and Cohort B – atorvastatin 20 mg or equivalent).
- Disease risk category (low, moderate, high, and very high risk, referred to Section 4.1).

### 6.3.3 Blinding

A double-blinding technique with in-house blinding will be used. A double-dummy design is used because the identity of MK-0653C and comparator (atorvastatin) cannot be disguised due to different appearance. The participant, the investigator, and Sponsor personnel or delegate(s) who are involved in the study intervention administration or clinical evaluation of the participants are unaware of the intervention assignments.

## 6.4 Study Intervention Compliance

Interruptions from the protocol-specified treatment plan needs to be documented, for those interruption  $\geq$ 25% from the treatment plan will require consultation between the investigator and the Sponsor and written documentation of the collaborative decision on participant management.

## 6.5 Concomitant Therapy

Medications or vaccinations specifically prohibited in the exclusion criteria are not allowed during the ongoing study. If there is a clinical indication for any medications or vaccinations specifically prohibited, discontinuation from study intervention may be required. The investigator should discuss any questions regarding this with the Sponsor Clinical Director. The final decision on any supportive therapy or vaccination rests with the investigator and/or the participant's primary physician. However, the decision to continue the participant on study intervention requires the mutual agreement of the investigator, the Sponsor, and the participant.

Specific restrictions are listed in [Table 4](#) for concomitant therapy or vaccination:

Table 4 Prohibited Medications

Exclusion	Class	Details	Prohibition Start	Note
18	CYP3A4 modulators	Cyclosporine; Systemically administered azole antifungals such as ketoconazole, fluconazole, and itraconazole; Macrolide antibiotics (e.g., clarithromycin, erythromycin); Protease inhibitors (e.g., ritonavir, saquinavir, lopinavir); Grapefruit or juice of grapefruit (the amount should not be over 200 ml/day, and should not be consumed 3 consecutive days or longer).	V1	
19	Cyclical hormones and Non-cyclical hormones	Cyclical hormones (cyclical oral contraceptives, cyclical hormone replacement) including the combination of ethinyl estradiol, norehisterone; Non-cyclical hormone therapy (including non-cyclical hormone replacement therapy or any estrogen antagonist/agonist).	V1	If the participant takes cyclical hormones (e.g., cyclical oral contraceptives, cyclical hormone replacement), including the combination of ethinyl estradiol and norethisterone, or non-cyclical hormones, including non-cyclical hormone replacement therapy or any estrogen antagonist/agonist, these treatment should be stably taken more than 8 weeks and supposed to be taken at the same dosage
20	Corticosteroids	Systemic corticosteroids (intravenous, intramuscular and oral steroids)	V1	Topical, intra-articular, nasal, inhaled and ophthalmic steroid therapies are allowed.
21	Agents potentially affect serum lipids	psyllium, other fiber-based laxatives, phytosterol margarine, herbal medicine and/or over the counter (OTC) therapies	8 weeks prior to V1	If the participant has been treated with a stable regimen for > 8 weeks prior to Visit 1 and agree to continue this regimen for the duration of the trial, concomitant therapy is acceptable.

Exclusion	Class	Details	Prohibition Start	Note
22	Anti-obesity drug	Mazindol	12 weeks prior to V1	
23	warfarin	Warfarin or warfarin-like anticoagulants and has not been on a stable dose with a stable INR.	V1	Warfarin or warfarin-like anticoagulants therapy is acceptable, if the participant must be on a stable dose with a stable INR for 6 weeks prior to Visit 1.
24	Lipid lowering agents	Cholestin TM, bile acid sequestrants, Ezetimibe, fibrates or niacin (>200 mg/day)	6 weeks prior to V1	
		Probucol	10 weeks prior to V1	
		Statin other than atorvastatin, Ezetimibe other than the ezetimibe component of MK-0653C	V1	

### **6.5.1      Rescue Medications and Supportive Care**

No rescue or supportive medications are specified for use in this study.

### **6.6      Dose Modification (Escalation/Titration/Other)**

No dose modifications are planned for this study.

### **6.7      Intervention After the End of the Study**

There is no study-specified intervention following the end of the study.

### **6.8      Clinical Supplies Disclosure**

The emergency unblinding call center will use the intervention/randomization schedule for the study to unblind participants and to unmask study intervention identity. The emergency unblinding call center should only be used in cases of emergency (see Section 8.1.11). In the event that the emergency unblinding call center is not available for a given site in this study, the central electronic intervention allocation/randomization system (IRT) should be used to unblind participants and to unmask study intervention identity. The Sponsor will not provide random code/disclosure envelopes or lists with the clinical supplies.

Each study site will be supplied by Sponsor with the investigational treatment.

## 6.9 Standard Policies

Trial site personnel will have access to a central electronic treatment allocation/randomization system (IRT system) to allocate participants, to assign treatment to participants and to manage the distribution of clinical supplies. Each person accessing the IRT system must be assigned an individual unique participant identification number (PIN). They must use only their assigned PIN to access the system, and they must not share their assigned PIN with anyone.

## 7 DISCONTINUATION OF STUDY INTERVENTION AND PARTICIPANT WITHDRAWAL

### 7.1 Discontinuation of Study Intervention

Discontinuation of study intervention does not represent withdrawal from the study.

As certain data on clinical events beyond study intervention discontinuation may be important to the study, they must be collected through the participant's last scheduled follow-up, even if the participant has discontinued study intervention. Therefore, all participants who discontinue study intervention prior to completion of the protocol-specified treatment period will still continue to participate in the study as specified in Section 1.3 and Section 8.11.4.

Participants may discontinue study intervention at any time for any reason or be discontinued from the study intervention at the discretion of the investigator should any untoward effect occur. In addition, a participant may be discontinued from study intervention by the investigator or the Sponsor if study intervention is inappropriate, the study plan is violated, or for administrative and/or other safety reasons. Specific details regarding procedures to be performed at study intervention discontinuation are provided in Section 8.1.10.

A participant must be discontinued from study intervention but continue to be monitored in the study for any of the following reasons:

- The participant or participant's legally acceptable representative requests to discontinue study intervention.
- The participant has a medical condition or personal circumstance which, in the opinion of the investigator and/or Sponsor, placed the participant at unnecessary risk from continued administration of study intervention.
- The participant has a confirmed positive serum pregnancy test.
- Consecutive (2 or more measurements within 1 week) elevations in ALT or AST  $\geq 3 \times$  ULN.

- Consecutive(2 or more measurements within 1 week) elevations in CK  $\geq 10$  x ULN with or without muscle symptoms.
- Consecutive (2 or more measurements within 1 week) elevations in CK  $\geq 5$  to  $< 10$  x ULN with muscle symptoms.
- The participant is requiring any treatment with telaprevir or fibrates.
- The participants are requiring any treatment with a potent inhibitor of cytochrome P450 3A4 (CYP3A4) such as, itraconazole, ketoconazole, erythromycin, clarithromycin or HIV protease inhibitors for their emerging medical conditions.
- Moved (or relocated): When the participant has either moved or relocated and is no longer able to participate in the trial.
- Participant developed a new condition which needs more intensive statin treatment or LDL-C lowing treatment.

For participants who are discontinued from study intervention but continue to be monitored in the study, all visits and procedures, as outlined in the SoA, should be completed.

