#### **8.1.10 Discontinuation and Withdrawal**

Participants who discontinue study intervention prior to completion of the predefined treatment period for any reason at any time can restart the study intervention. However, participants are expected to rechallenge the study intervention at the earliest time upon decision of the investigator, and all premature discontinued participants should be encouraged to continue to be followed for all remaining study visits, regardless of the rechallenge, as outlined in the SoA and Section 8.11.3.

When a participant withdraws from participation in the study, all applicable activities scheduled for the end of study visit should be performed (at the time of withdrawal). Any AEs that are present at the time of withdrawal should be followed in accordance with the safety requirements outlined in Section 8.4 and 8.11.

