#### **8.4.7 Events of Clinical Interest (ECIs)**

Selected nonserious and SAEs are also known as ECIs and must be reported to the Sponsor.

Events of clinical interest for this study include:

1. An elevated AST or ALT lab value that is greater than or equal to 3X the upper limit of normal and an elevated total bilirubin lab value that is greater than or equal to 2X the upper limit of normal and, at the same time, an alkaline phosphatase lab value that is less than 2X the upper limit of normal, as determined by way of protocol-specified laboratory testing or unscheduled laboratory testing.\*

\*Note: These criteria are based upon available regulatory guidance documents. The purpose of the criteria is to specify a threshold of abnormal hepatic tests that may require an additional evaluation for an underlying etiology. The study site guidance for assessment and follow-up of these criteria can be found in the Investigator Study File Binder (or equivalent).

2. An overdose of Sponsor's product, as defined in Section 8.5, that is not associated with clinical symptoms or abnormal laboratory results.
3. Myopathy, rhabdomyolysis, or if the CK criterion necessitating study medication discontinuation is met, the event should be reported as ECI because of their association with lipid-lowering treatments.

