  - **Time Course:** Did the AE follow in a reasonable temporal sequence from administration of the Sponsor's product? Is the time of onset of the AE compatible with a drug-induced effect (applies to studies with investigational medicinal product)?
  - **Likely Cause:** Is the AE not reasonably explained by another etiology such as underlying disease, other drug(s)/vaccine(s), or other host or environmental factors.
  - **Dechallenge:** Was the Sponsor's product discontinued or dose/exposure/frequency reduced?
    - If yes, did the AE resolve or improve?
    - If yes, this is a positive dechallenge.
    - If no, this is a negative dechallenge.
  - **Rechallenge:** Was the participant re-exposed to the Sponsor's product in this study?
    - If yes, did the AE recur or worsen?
    - If yes, this is a positive rechallenge.
    - If no, this is a negative rechallenge.

(Note: This criterion is not applicable if: (1) the AE resulted in death or permanent disability; (2) the AE resolved/improved despite continuation of the Sponsor's product; (3) the study is a single-dose drug study; or (4) Sponsor's product(s) is/are only used 1 time.)

- **Rechallenge:** Was the participant re-exposed to the Sponsor's product in this study?
  - If yes, did the AE recur or worsen?
  - If yes, this is a positive rechallenge.
  - If no, this is a negative rechallenge.

(Note: This criterion is not applicable if: (1) the initial AE resulted in death or permanent disability, or (2) the study is a single-dose drug study; or (3) Sponsor's product(s) is/are used only 1 time.)

NOTE: IF A RECHALLENGE IS PLANNED FOR AN AE THAT WAS SERIOUS AND MAY HAVE BEEN CAUSED BY THE SPONSOR'S PRODUCT, OR IF RE-EXPOSURE TO THE SPONSOR'S PRODUCT POSES ADDITIONAL POTENTIAL SIGNIFICANT RISK TO THE PARTICIPANT THEN THE RECHALLENGE MUST BE APPROVED IN

ADVANCE BY THE SPONSOR CLINICAL DIRECTOR, AND IF REQUIRED, THE IRB/IEC.

- **Consistency with study intervention profile:** Is the clinical/pathological presentation of the AE consistent with previous knowledge regarding the Sponsor's product or drug class pharmacology or toxicology?
- The assessment of relationship will be reported on the case report forms/worksheets by an investigator who is a qualified physician according to his/her best clinical judgment, including consideration of the above elements.
- Use the following scale of criteria as guidance (not all criteria must be present to be indicative of a Sponsor's product relationship).

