	Simvastatin 20-40 mg
	Xuezhikang 1.2 g

\*Studies of atorvastatin (80 mg) among the Chinese population are limited; please use with caution. LDL-C: low-density lipoprotein cholesterol.

Although Xuezhikang capsules are classified as a lipidlowering Chinese medicine, their lipid-lowering mechanism is similar to that of statins. These capsules are refined via the biological fermentation of a special monascus added to rice using the modern GMP standard manufacturing process. The main ingredients of these capsules include 13 types of natural statin compounds, including lovastatin without a crystal structure and its homologs. The commonly used dose is 0.6 g twice per day. The China Coronary Secondary Prevention Study (CCSPS) and other clinical studies confirmed that Xuezhikang capsules reduce cholesterol and significantly reduce the overall mortality of patients with coronary heart disease, the incidence of cardiovascular events, and number of side effects.

Most people show excellent tolerance to statins. Adverse reactions are primarily observed in patients who receive large doses of statin therapy. The most common manifestations are discussed below.

(1) Abnormal liver function. The main presentation of this condition is the increase of transaminases. The incidence is approximately 0.5%-3%, and it shows dose dependence. Patients with an increase of serum alanine aminotransferase (A), aspartate aminotransferase (AST) higher than three times the upper limit of normal values, and the combined increase of total bilirubin should reduce or discontinue drug use. Patients with an increase of transaminases within three times of the upper limit of normal values can be observed based on the original doses or reduced doses. Some patients can restore normal transaminases after

this treatment. The application contraindications of statins are decompensated cirrhosis and acute liver failure.

(2) Statin-related adverse muscle reactions include myalgia, myositis, and rhabdomyolysis. When patients have muscle discomfort, weakness, or both and continuous creatine kinase detection shows progressive increases, statins doses should be reduced or the drugs should be discontinued.

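### A single combined ALT/AST–bilirubin result triggers reporting but no objective drug stop until ALT/AST is confirmed, and restart afterwards has no liver condition

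*Combined protocol and SAP*

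**What the plan says.** Section 7.1 lists the reasons for which study intervention must be stopped. The liver entry is "Consecutive (2 or more measurements within 1 week) elevations in ALT or AST" of 3 x ULN or more. Neither bilirubin nor ALP appears. A separate entry in the same list covers a condition that, in the opinion of the investigator and/or Sponsor, "placed the participant at unnecessary risk from continued administration of study intervention".

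Section 8.4.7 item 1 makes ALT or AST of at least 3 x ULN, with "an elevated total bilirubin lab value that is greater than or equal to 2X the upper limit of normal" and ALP below 2 x ULN, an event of clinical interest. Table 5 requires potential drug-induced liver injury to be reported within 24 hours. The note to item 1 says the pattern may call for further evaluation, and adds: "The study site guidance for assessment and follow-up of these criteria can be found in the Investigator Study File Binder". No drug action is stated.

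On restart, section 8.1.10 lets a participant who discontinued for whatever reason resume, and says "participants are expected to rechallenge the study intervention at the earliest time upon decision of the investigator". The Appendix 3 rechallenge note requires advance approval by the Sponsor Clinical Director if the event was serious and possibly caused by the product, or if re-exposure "POSES ADDITIONAL POTENTIAL SIGNIFICANT RISK TO THE PARTICIPANT THEN THE RECHALLENGE MUST BE APPROVED IN" advance.

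The guideline reproduced in Appendix 7 (its section 10.1.1) says that patients with transaminases above three times the upper limit and "the combined increase of total bilirubin should reduce or discontinue drug use". Section 6.6 states: "No dose modifications are planned for this study".

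**The concern.** The protocol singles out the combined pattern for expedited reporting, and Table 7 makes nearly the same pattern a Tier 1 safety endpoint with no requirement for consecutive values. The stopping list does not pick it up. A participant with one such result has no rule-based stop until ALT or AST is found raised again within a week, and the protocol gives no date by which that second sample must be taken.

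The restart wording leans towards early re-exposure and makes no exception for a liver signal. What is at stake is the safety of the few participants who show the pattern. Visit 6 ends treatment, so Week 6 is the only scheduled liver test on randomized drug with dosing still to come.

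**Working it through.** There is no plan figure to reproduce. The check is one of logic, followed by timing and expected counts.

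**1. When does the existing stop catch the pattern?** Every item 1 case has ALT or AST of at least 3 x ULN by definition.
- If a second value within 1 week is again at least 3 x ULN, the 7.1 liver stop applies whatever the bilirubin.
- If the repeat is not yet done, comes after 1 week, or falls below 3 x ULN, no objective stop applies. Only the judgement-based entries remain.

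**2. Can scheduled tests supply the confirmation?** The Schedule of Activities sets Visit 5 at Week 6 ±7 days and Visit 6 at Week 12 ±7 days, both counted from Visit 4.
- Visit 5: day 42 ± 7 = days 35 to 49. Visit 4 to Visit 5 is therefore 35 to 49 days.
- Visit 6: day 84 ± 7 = days 77 to 91.
- Visit 5 to Visit 6: shortest 77 − 49 = 28 days, nominal 84 − 42 = 42, longest 91 − 35 = 56.

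The rule needs two values within 7 days, so only an unscheduled repeat can satisfy it. Section 8.3.4 asks for repeats of clinically significant abnormal values but sets no deadline.

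**3. What may happen after a stop?** Section 8.1.10 permits restart after any discontinuation on the investigator's decision. The Appendix 3 approval applies only if one of its two conditions is met. Section 8.4.7 describes events of clinical interest as including nonserious ones, so an item 1 event does not automatically meet the first condition; the second is itself a judgement.

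**4. How often?** The documents give no rate for the combined pattern. The 0.5%–3% in Appendix 7 is for raised transaminases and is not used. The rate below, for the pattern newly appearing at Week 6, is an assumption with no source in the documents. The number tested runs from 450 × 0.9 = 405 (all of the planned 10% drop-out lost before Week 6) to 450.

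| Assumed rate | Expected cases (405; 450) | Chance of at least one, 1 − (1 − rate)^n |
|---|---|---|
| 0.01% | 0.0405; 0.045 | 4.0%; 4.4% |
| 0.1% | 0.405; 0.45 | 33%; 36% |

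**The case against.** The strongest reply is that the plan already handles such a case. The existing stop needs no bilirubin rise, which makes it broader, and its one-week wording is evidently meant for a prompt repeat. Section 8 allows unscheduled safety samples and local laboratories. Appendix 3 obliges the investigator to arrange additional tests when medically indicated or when the Sponsor asks. The Sponsor hears within 24 hours, and Appendix 2 leaves safety results unblinded to the investigator. Either party can stop drug on one sample under the unnecessary-risk entry. The site binder may also time the repeat or interrupt dosing. A potential liver-injury case would plausibly meet the Appendix 3 condition for prior approval of rechallenge.

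Most of this stands, and it rules out several stronger readings that a reader might infer:
- *That no objective stop covers the pattern.* Once ALT/AST is confirmed within a week, one does.
- *That a participant would go 28 to 56 days on drug unreviewed.* Those figures are the spacing of scheduled draws, not an expected delay.
- *That the protocol contradicts its own guideline appendix.* The guideline says to reduce or discontinue, and with no dose change planned only discontinuation is left. But it gives no bilirubin cutoff, no timing and no single-sample rule, and the protocol uses it for diagnosis, risk category, goals and lifestyle, not for stopping.
- *That 4% to 36% is a chance of harm.* It is the chance of seeing any case at Week 6 under an assumed rate. Cases left unconfirmed and unstopped are a smaller fraction, which cannot be estimated here.

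What the reply does not supply is a written trigger for stopping on the first combined result, a deadline for the repeat, or a restart condition in 8.1.10.

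**Conclusion.** The point holds in a limited form. Between a first combined result and its confirmation, stopping depends on investigator or Sponsor judgement, or on binder guidance not seen here. Restart afterwards is also mainly a matter of judgement, under wording that favours early re-exposure. If the binder already sets a stop and a repeat deadline, what remains is to bring them into the protocol.

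The expected frequency is low: 0.04 to 0.45 cases at Week 6, wholly dependent on the assumed 0.01%–0.1%. The argument rests on the seriousness of each case and the small cost of a rule, not on numbers. The documents support no effect on the LDL-C comparison. This is a cheap safety improvement, not a defect in the analysis.

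**What to change.** Add to the mandatory list in 7.1:

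> *The criteria in 8.4.7 item 1 are met on a single test. Study intervention is stopped at once, and ALT, AST, total bilirubin and ALP are repeated within 7 days. It is not restarted unless these values have returned to normal or baseline, a cause other than study drug is documented, and the Sponsor Clinical Director approves in advance (Appendix 3).*

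Add a cross-reference to this entry in 8.4.7 item 1, and make the restart sentence in 8.1.10 subject to it. Check that the binder guidance agrees.

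The cost is these few lines and one extra chemistry sample per affected participant. The downside is an occasional unneeded stop. Section 9.6.1 excludes measurements taken more than 5 days after the last dose, so a participant stopped at Week 6 and not restarted contributes no Week 12 LDL-C. With fewer than 0.5 cases expected under the assumed rates, that is at most about one value in 450 (1/450 = 0.2%).
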